6.3 PATIENT SETS ANALYSED

The following nested patient sets are defined:

- Randomised set (RS):

This patient set includes all patients who signed informed consent form and were also randomised, regardless whether the patient was treated with study medication or not.

- Treated set (TS):

This patient set is nested within RS and includes all patients who were dispensed study medication and were documented to have taken any dose of study medication. TS will be used for patient disposition, demographics and baseline disease characteristics, concomitant therapies, treatment compliance, treatment exposure and safety analyses (including AEs and vital signs).

- Full analysis set (FAS):

This patient set is nested within TS and includes patients who had baseline measurement and at least one post-baseline measurement for the primary endpoint or secondary endpoints. Assignment to the FAS will be done after implementation of any data handling rules which set measurements to missing.

- Full analysis set excluding exacerbation (FAS-EE):

This patient set is nested within FAS and the data from patients who have had an exacerbation during the treatments will be excluded from this data set. FAS-EE will be used for the efficacy analyses.

- Per protocol set (PPS):

This patient set is nested within FAS-EE and includes only patients who had no important PVs which are specified to be excluded from the PPS (Table 6.3: 1).

The final decision regarding which patients are excluded from PPS will be made at BRPM or data base lock meeting (DBLM) prior to data unblinding.

Table 6.3: 1 Patient sets analysed

		Patient Sets
Class of endpoint	TS	FAS-EE
Primary endpoint		primary analysis
Secondary endpoints		X
Safety endpoints	X	
Demographic/baseline endpoints/exposure	X	

6.5 POOLING OF CENTRES

This section is not applicable because centre/country is not included in the statistical model.

6.6 HANDLING OF MISSING DATA AND OUTLIERS

As noted in the protocol, in general, missing data at a given visit will be imputed by the available data from the patient at that visit and completely missing visits will be handled through the statistical model.

Completely missing visits will not be imputed and will stay as missing, and will be handled in the mixed model repeated measures model.

It could happen that a patient needed therapy for COPD symptoms at a clinic visit. This therapy was entered on the rescue medication electronic Case Report Form (eCRF). This may or may not be the rescue medication provided by Boehringer Ingelheim (BI). For purposes of the imputation rules this will be termed “rescue medication” regardless of whether or not it was BI-supplied rescue medication.

The following rules will be used for spirometry data which were collected at Visits 2, 3 and 4:

- Since there is only one spirometry measurement at each on-treatment clinic visit, rescue medication use on or before the spirometry measurement or rescue use with unknown time will both result in all spirometry measurements for the visit being set to missing.

- Randomly missing spirometry measurements at Visits 2, 3, and 4, e.g., due to a mechanical failure, will not be imputed.

The rules used for spirometry data will also be applied to Body Plethysmography. CMR data will not be imputed.

Missing or incomplete AE dates are imputed according to BI standards (see “Handling of missing and incomplete AE dates”) (3).

6.7 BASELINE, TIME WINDOWS AND CALCULATED VISITS

Baselines for Primary Endpoint

The primary endpoint is change from baseline in LVEDVI in the 6th week of treatment with tiotropium+olodaterol FDC versus fluticasone propionate+salmeterol FDC.

- The baseline is defined as the (pre-dose) measurement of the LVEDVI performed in a week prior to Visit 2 (or prior to dosing on the Visit 2).

Baseline for endpoints not related to CMR is defined as the pre-dose measurement at Visit 2.

Time windows and calculated visits

Planned and actual study day will be included in the analysis data sets. These will both be calculated relative to the beginning of the study and to the beginning of respective study periods in the crossover design as indicated in the following table.

Table 6.7: 1 Planned and actual study days

Visit	Relative to period start		Relative to study start	
	Planned day	Actual day	Planned day	Actual day
2	1	1	1	1
3	43	Visit 3 date - Visit 2 date + 1	43	Visit 3 date - Visit 2 date + 1
4	43	Visit 4 date - Visit 3 date + 1	85	Visit 4 date - Visit 2 date + 1

7. PLANNED ANALYSIS

For End-Of-Text tables, the set of summary statistics is: N / Mean / Standard deviation (SD) / Min / Median / Max.

Tabulations of frequencies for categorical data will include all possible categories and will display the number of observations in a category as well as the percentage (%) relative to the respective treatment group (unless otherwise specified, all patients in the respective patient set whether they have non-missing values or not). Percentages will be rounded to one decimal place. The category missing will be displayed only if there are actually missing values.

7.1 DEMOGRAPHIC AND OTHER BASELINE CHARACTERISTICS

Only descriptive statistics are planned for this section of the report.

7.2 CONCOMITANT DISEASES AND MEDICATION

Only descriptive statistics are planned for this section of the report.

Use of pulmonary medications during treatment period and testing will be summarised in the end-of-text tables in the Clinical Trial Report (CTR) and a subject data listing of all concomitant medications will be provided in Appendix 16.2.

A table of number (%) of patients with concomitant diagnoses by system organ class (SOC) and preferred term (PT) will be included along with a supporting subject data listing. Concomitant diagnoses will be coded with the most recent version of the Medical Dictionary for Regulatory Activities (MedDRA) in effect at database lock.

Descriptive statistics and frequency tables (%) will be presented for history of trial indication.

Frequency tables (%) will be presented for COPD background characteristics.

7.3 TREATMENT COMPLIANCE

Only descriptive statistics are planned for this section of the report. Only descriptive statistics, i.e. the number (%) and percent of patients with compliance in the range of 80% - 120% will be provided. (cf. [Section 5.4](#) for calculation of treatment compliance).

7.4 PRIMARY ENDPOINT(S)

In the primary analysis, the two-sided hypothesis as given in Section 7.2 in the CTP will be tested based on adjusted mean change from baseline in LVEDVI, as listed in Section 5.1.1 in the CTP, using a restricted maximum likelihood (REML)-based MMRM. This model will include treatment and period as fixed effects, patient as a random effect and baseline as covariate. Unstructured covariance structure will be used for within patient variation. If convergence is not achieved, the compound symmetry covariance structure will be used. The SAS procedure MIXED will be used involving the restricted maximum likelihood estimation and the Kenward-Roger approximation for denominator degrees of freedom. This approach is described in [\(2\)](#). Adjusted mean values as well as treatment contrasts will be presented together with the 95% confidence intervals (CI) and p-values. The primary analysis will be performed on FAS-EE.

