Statistical methods:	
Restricted Maximum Likelihood (REML) estimation based Mixed-effects Model for Repeated Measures (MMRM) analysis will be used to obtain adjusted means for the treatment effects.          This model will include treatment and period as fixed effects, patient as a random effect and baseline as a covariate. (Unstructured covariance structure will be used for within patient variation).
 
Descriptive statistics for the safety analyses/assessment.
		

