## 5. VARIABLES AND THEIR ASSESSMENT

### 5.1 TRIAL ENDPOINTS

#### 5.1.1 Primary Endpoint(s)

The primary endpoint is change from baseline in LVEDVI in the 6th week of treatment with tiotropium+olodaterol FDC versus fluticasone propionate+salmeterol FDC.

LVEDVI is normalized left ventricular end diastolic volume (LVEDV), divided by body surface area (BSA) ([Appendix 10.3](#)).

Baseline is defined as the value obtained during the assessment performed in a week prior to Visit 2. The change from baseline is calculated as the value obtained in a week prior to Visits 3 and 4 (end of each treatment periods) minus the baseline value.

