## 7. STATISTICAL METHODS AND DETERMINATION OF SAMPLE SIZE

### 7.1 STATISTICAL DESIGN - MODEL

This is an exploratory, randomised, double-blind, double-dummy, active-controlled, two period complete cross-over study to investigate the effect of 6 weeks treatment of orally inhaled tiotropium + olodaterol FDC (5 µg/5 µg) compared with fluticasone propionate + salmeterol FDC (1000 µg /100 µg) on left ventricular function and arterial stiffness in patients with COPD.

Based on these design considerations, a mixed effect repeated measures model (MMRM) with treatment and period as fixed effects and patient as a random effect will be used for the primary analysis. Detailed specifications are provided in [Section 7.3](#).

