### 7.3.1 Primary endpoint analyses

In the primary analysis, the two-sided hypothesis as given in [Section 7.2](#) will be tested based on adjusted mean change from baseline in LVEDVI, as listed in [Section 5.1.1](#), using a restricted maximum likelihood (REML)-based MMRM. This model will include treatment and period as fixed effects, patient as a random effect and baseline as covariate. Unstructured covariance structure will be used for within patient variation. If convergence is not achieved, the compound symmetry covariance structure will be used. The SAS procedure MIXED will be used involving the restricted maximum likelihood estimation and the Kenward-Roger approximation for denominator degrees of freedom. This approach is described in [[R10-4391](#)]. Adjusted mean values as well as treatment contrasts will be presented together with the 95% confidence intervals (CI) and p-values.

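### Does pairing a random patient effect with an unstructured covariance leave the primary model undefined?

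*SAP*

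**What the plan says.** After the fixed terms for treatment and period, SAP 7.4 continues: "patient as a random effect and baseline as covariate. Unstructured covariance structure will be used for within patient variation". The only alternative offered, worded identically in Protocol 7.3.1, is "If convergence is not achieved, the compound symmetry covariance structure will be used". On estimation, the SAP states: "The SAS procedure MIXED will be used involving the restricted maximum likelihood estimation and the Kenward-Roger approximation for denominator degrees of freedom".

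The protocol synopsis has the same pairing, with the covariance sentence in parentheses directly after the mention of the random effect: "patient as a random effect and baseline as a covariate. (Unstructured covariance structure will be used for within patient variation". Protocol 7.1 names only "treatment and period as fixed effects and patient as a random effect will be used for the primary analysis" and leaves the details to 7.3.

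The number of outcome values per patient follows from Protocol 5.1.1: "The change from baseline is calculated as the value obtained in a week prior to Visits 3 and 4", less a single baseline. That gives two outcomes, and the baseline scan also serves as the covariate. Protocol 7.3.2 and SAP 7.5.2 use the same model for the secondary endpoints. Neither document contains SAS code or says whether the random effect is a separate term alongside the residual covariance.

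**The concern.** A 2×2 covariance matrix has three free elements. An unstructured residual matrix already uses all three, so a patient variance on top makes a fourth. Compound symmetry already contains a common covariance, so a patient variance on top of it repeats the same quantity. In both models the information matrix for the covariance parameters is singular.

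Three things would then be at stake:

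- The convergence rule could be triggered by over-specification instead of by the data, and it would lead to a model with the same redundancy.
- The Kenward-Roger method uses the inverse of that information matrix, which does not exist in the ordinary sense.
- An analyst might have to choose a model after seeing fit messages. The choice could matter, because the unstructured and compound-symmetry fits need not give the same treatment estimate.

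**Working it through.** **The plan's own figure.** Protocol 7.7 gives 74 patients for 80% power at a difference of 2.5 mL/m² and SD 7.5. A noncentral-t calculation for a two-period crossover, with 7.5 taken as the SD of the within-patient difference and 72 df, gives power 0.808 at N = 74. The same method reproduces all six rows of Table 7.7:1 (52, 68, 74, 98, 74, 98). The figure does not depend on how the covariance is parameterised.

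**Counting parameters.** Let s be the patient variance and r11, r22, r12 the unstructured residual terms. Then

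V11 = s + r11, V22 = s + r22, V12 = s + r12.

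Four parameters map to three quantities; the Jacobian and the information matrix both have rank 3. Raising s by any amount and lowering all three residual terms by the same amount leaves V unchanged.

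For the fallback, with common covariance c and residual variance e,

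V11 = V22 = s + c + e, V12 = s + c.

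Three parameters map to two quantities, with rank 2. The literal redundancy is confirmed in both models.

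**What the redundancy touches.** The fixed effects and their model-based SEs depend on the covariance parameters only through V, and V is identified. A patient with one period only contributes to V11 or V22, so incomplete data do not alter this.

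A simulated AB/BA trial shows it. The assumed inputs were 37 patients per sequence, true difference 2.5, residual SD 7.5/√2 = 5.30, patient SD 5, period effect 0.5, and baseline mean 65, SD 12 and slope −0.3. The REML estimate of V was V11 = 36.496, V22 = 49.148, V12 = 9.594. Moving along the ridge:

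| s | r11 | r22 | r12 | −2 REML log-lik. | Estimate | SE |
|---|---|---|---|---|---|---|
| 0 | 36.496 | 49.148 | 9.594 | 701.5157 | 2.8404 | 0.9369 |
| 10 | 26.496 | 39.148 | −0.406 | 701.5157 | 2.8404 | 0.9369 |
| 25 | 11.496 | 24.148 | −15.406 | 701.5157 | 2.8404 | 0.9369 |

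The row s = 0 is the unstructured fit with no random effect. By s = 30 the residual matrix has a negative eigenvalue (−8.54), so the ridge of valid solutions ends between 25 and 30. For compound symmetry, every split between s and c gave 703.1862, estimate 2.6941 and SE 0.9477.

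**Degrees of freedom.** Write the identified quantities as Jθ, with J of full row rank, and let I be their information matrix. The information for θ is J′IJ, which is singular. Kenward-Roger uses its inverse only through J(J′IJ)⁻J′, and this equals I⁻¹ for any generalised inverse. Both structures are linear in their parameters, so the second-derivative term of the adjustment is zero. The adjusted SE and the df are therefore those of the model without the redundant term. REML fits using a generalised inverse agreed: estimate, SE and Satterthwaite-type df were the same with and without the random effect, and all fits converged in a few iterations.

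**Unstructured against compound symmetry.** In the example the two estimates differ by 2.8404 − 2.6941 = 0.146 mL/m². Across simulated 74-patient trials, 95% of such differences lay within about 0.21 to 0.23 with equal period variances, and 5% significance disagreed in about 2% of trials. With the total period-2 SD 30% larger, the figures were about 0.65 and 8 to 10%; with only the residual SD 30% larger, 0.45 and 5%. The documents give no period-specific SD, so the 30% is an assumption. Under the null, rejection was 4.4 to 4.9% (unstructured) and 4.9 to 5.1% (compound symmetry).

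These differences come from allowing or forbidding unequal period variances. They would be the same if the random effect were deleted and the fallback kept.

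**The case for a change.** The strongest case for a change is procedural. This is the primary analysis, and SAP Section 3 says the document gives more technical detail than the protocol, yet 7.4 repeats the protocol wording. Two programmers could code it differently. A redundant parameter can produce a Hessian warning or a failure to converge, and the written rule would then move to compound symmetry for a reason unrelated to the data. The clarification would cost one line.

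Part of this stands. The wording is literally redundant, and a spurious message is possible; no SAS run was made that excludes it. But no run shows the redundancy triggering the fallback either, and if the software sets one component to zero, the result is exactly the unstructured fit. If the fallback were invoked, it is prespecified, it held its type I error in the scenarios above, and its own redundancy is equally inert.

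There is also a natural reading with no redundancy. The plan calls this a repeated-measures model, and the synopsis places the covariance sentence in parentheses after the random effect, as though explaining how correlation within a patient is handled. On that reading patient is simply the subject of one covariance matrix. A programmer who follows it and one who follows the literal text reach the same estimate and interval.

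**Conclusion.** No change follows, because there is nothing to gain. The model as worded has one covariance parameter too many, both in the primary form (rank 3 of 4) and in the fallback (rank 2 of 3). Within each structure the effect on the treatment estimate and its SE is nil: 2.840 and 0.937 with or without the random effect in the worked example. The degrees of freedom are also unchanged, provided the software uses a generalised inverse or sets the redundant component to zero. The sample size is unaffected.

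The differences between the unstructured and compound-symmetry fits belong to any plan that names one as fallback for the other, so they are not evidence against this wording. The remaining risk is a nuisance message from the software, followed by a fallback that is prespecified and valid in the scenarios examined. The trial is exploratory and its secondary p-values are descriptive, so that risk does not warrant an amendment.

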7.5 SECONDARY ENDPOINT(S)

7.5.1 Key secondary endpoint(s)

This section is not applicable as no key secondary endpoint has been specified in the protocol.

7.5.2 (Other) Secondary endpoint(s)

The MMRM described for the primary endpoint will be performed for secondary continuous endpoints. Adjusted mean values as well as treatment contrasts will be presented together with the 95% CIs and nominal p-values. All p-values will be considered as descriptive.

7.7 EXTENT OF EXPOSURE

Extent of exposure is calculated as drug stop date minus drug start date plus one day and treatment interruptions are not taken into account in the calculation.

Extent of exposure will be summarised using descriptive statistics for the total treatment exposure in days as well as tabulation of number of patients with total exposure fall into the following categories:

- 1 day
- 2 – 21 days
- 22 – 42 days
- 43 – 63 days
- 64 - 84 days
- ≥ 85 days.

Extent of exposure will also be summarised using descriptive statistics into the following categories:

- 1 – 39 days
- 40 – 46 days
- ≥ 47 days.

7.8 SAFETY ANALYSIS

All safety analyses will be performed on the treated set.

7.8.1 Adverse events

Unless otherwise specified, the analyses of adverse events will be descriptive in nature. All analyses of AEs will be based on the number of subjects with AEs and NOT on the number of AEs.

For analysis multiple AE occurrence data on the CRF will be collapsed into an AE provided that all of the following applies:

- All AE attributes are identical ((LLT, intensity, action taken, therapy required, seriousness, reason for seriousness, relationship, outcome).

- The occurrences were time-overlapping or time-adjacent (time-adjacency of 2 occurrences is given if the second occurrence started on the same day or on the day after the end of the first occurrence).

For further details on summarization of AE data, please refer to [\(3, 4\)](#).

The analysis of adverse events will be based on the concept of treatment emergent adverse events. That means that all adverse events occurring between first drug intake till last drug intake + residual effect period will be assigned to the randomised treatment. All adverse events occurring before first drug intake will be assigned to ‘screening’ and all adverse events occurring after the residual effect period will be assigned to ‘post-treatment’ (for listings only). For details on the treatment definition, see [Section 6.1](#).

According to ICH E3 [\(5\)](#), AEs classified as ‘other significant’ needs to be reported and will include those non-serious and non-significant adverse events with

- (i) ‘action taken = discontinuation’ or ‘action taken = reduced’, or
- (ii) marked haematological and other lab abnormalities or lead to significant concomitant therapy as identified by the Clinical Monitor/Investigator at a Medical Quality Review Meeting.

An overall summary of adverse events will be presented.

The frequency of subjects with adverse events will be summarised by treatment, primary system organ class and preferred term (mention MedDRA levels to be displayed in the tables). Separate tables will be provided for subjects with other significant adverse events according to ICH E3 [\(5\)](#), for subjects with adverse events of special interest (only if defined), for subjects with serious adverse events, for subjects with adverse events leading to discontinuation, for subjects with drug-related adverse events, and for subjects with related serious adverse events.

The system organ classes will be sorted alphabetically, preferred terms will be sorted by frequency (within system organ class).

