### 5.3.6.2 Adverse event collection and reporting

#### **AE Collection**

The Investigator shall maintain and keep detailed records of all AEs in their patient files.

The following must be collected and documented on the appropriate CRF(s) by the Investigator:

- From signing the informed consent onwards through the Residual Effect Period (REP), until individual patient's end of trial:
  - All AEs (serious and non-serious).
- After the individual patient's end of trial:
  - The Investigator does not need to actively monitor the patient for AEs but should only report relevant SAEs and relevant AESIs of which the Investigator may become aware of.

[figure not shown]

Figure 5.3.6.2: 1 AE collection in 1237.36

The REP is defined as 21 days after the last trial medication application. All AEs which occurred through the treatment phase and throughout the REP will be considered as on treatment please see [Section 7.3.4](#). Events which occurred after the REP will be considered as post treatment events.

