### 7.3.4 Safety analyses

Adverse events will be coded using the Medical Dictionary for Regulatory Activities (MedDRA) coding dictionary. Standard BI summary tables and listings will be produced. All adverse events with an onset between start of treatment and end of the residual effect period (REP), a period of 21 days after the last dose of trial medication, will be considered 'treatment-emergent'. Adverse events that start before first drug intake and deteriorate under treatment will also be considered as 'treatment-emergent'. Adverse events with an onset from the start of treatment to Visit 3 will be assigned to the first treatment, and adverse events with an onset on a day after Visit 3 to the end of REP to the second treatment.

All treated patients will be included in the safety analysis. In general, safety analyses will be descriptive in nature and will be based on BI standards. No hypothesis testing is planned.

Frequency, severity, and causal relationship of adverse events will be tabulated by system organ class and preferred term after coding according to the current version of the MedDRA.

Blood pressure and pulse rate measured in conjunction with PFT testing will be presented for each treatment using descriptive statistics.

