4. CHANGES IN THE PLANNED ANALYSIS OF THE STUDY

All analyses described in the TSAP are outlined in the CTP.

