6. GENERAL ANALYSIS DEFINITIONS

6.1 TREATMENT(S)

The doses to be administered are described in Section 4 of the CTP.

This is a crossover trial consisting of a one to three-week run-in period followed by two six-week treatment periods and a three-week post-treatment period. The day after the follow-up visit will be considered the start of the post-study period in case there are any subsequent AE data we become aware of. In this study, there will be no washout between treatment periods.

In general, the first period will be considered last until 12 hours after the last intake of medication assigned for the first period, then the second period will start

For the main safety analysis, data occurring during the treatment periods and within 21 days of stop of study drug for that period will be assigned to the respective treatment for that period. Data occurring before the first drug intake date is assigned to "screening". If the next treatment period starts within 21 days of the end of the last period, data after the start of treatment for the next period will be assigned to the treatment for that period. In this trial, next treatment will be started after end of treatment of first period as soon as possible because there is no washout period planned. The last day of the first period is the day of the last intake of medication for the first period. AEs occurring at the last day of the first period will be assigned to the first period even if the medication of the evening dose already belongs to the second period. Data more than 21 days after drug stop date for a period but before the start of the next period will be assigned to washout. Data more than 21 days after the end of the last treatment period and up to and including the date of the study termination will be assigned to follow-up.

Any cases of patient being treated with the wrong study medication will be identified and summarised as an important protocol violation (PV).

- If a patient was treated with a treatment sequence different from the randomised treatment sequence throughout the on-treatment period, i.e., a patient was treated with incorrect study medication during every treatment period, this patient will be included in the treated set and will be analysed as treated for both efficacy and safety analyses, including patient disposition. Such a case will be reported as an important PV and this patient will be excluded from the per-protocol set (PPS).

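### SAP 6.1 and 7.8.1 place every pre-dose adverse event in screening, omitting the protocol's rule for events that worsen on treatment, so treatment-emergent events may be under-counted

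*SAP*

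**What the plan says.** Protocol 7.3.4 defines treatment-emergent events in two parts. The first covers events whose onset lies between the start of treatment and the end of the residual effect period (REP), which is 21 days after the last dose. The second extends this: "Adverse events that start before first drug intake and deteriorate under treatment will also be considered as" treatment-emergent. The protocol then divides events between the two treatments by onset: up to Visit 3 to the first, on a later day to the second.

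SAP 7.8.1 says that it follows the treatment-emergent concept and explains it by the first part alone: "That means that all adverse events occurring between first drug intake till last drug intake + residual effect period will be assigned to the" randomised treatment. It continues: "All adverse events occurring before first drug intake will be assigned to" screening. For details it refers to SAP 6.1, which says "Data occurring before the first drug intake date is assigned to" screening. Neither section makes an exception for worsening.

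SAP Section 4, where changes from the protocol belong, says "All analyses described in the TSAP are outlined in the CTP".

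**The concern.** The SAP gives an explicit rule that differs from the protocol's, so this is a conflict and not just missing detail. A programmer working from the SAP would label as screening an event that the protocol places in the treatment-emergent tables, and nothing in the SAP would alert a reader to the change.

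Pre-dose events will be in the database, because the protocol collects adverse events from informed consent onwards. Long-acting bronchodilators and inhaled corticosteroids are also withdrawn before baseline, so some events may still be open at first dose. SAP 7.8.1 plans separate tables for serious events, drug-related events and events leading to discontinuation. A run-in event that becomes serious, or leads to stopping, only after worsening on treatment is the kind of case that the protocol's second part would keep in those tables.

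**Working it through.** The plan states no figure on this point, so there is none to reproduce. The check compares the two definitions.

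**Step 1: the two sets.** Let A be events with onset from first intake to the end of the REP. Let B be events with onset before first intake that deteriorate under treatment.

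- Protocol 7.3.4: treatment-emergent = A together with B.
- SAP 6.1 and 7.8.1, reading an event as occurring at its onset: treatment-emergent = A. Events in B go to screening.

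**Step 2: direction.** A is contained in A together with B. On this reading the SAP count can only equal the protocol count or fall below it.

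**Step 3: what a loss requires.** All of these must hold:

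1. The event starts between consent and first dose.
2. It is still open at first dose.
3. It worsens on treatment.
4. The worsening stays in one record with the pre-dose onset date. SAP 7.8.1 merges occurrences only when every listed attribute matches, including intensity. A worsening entered separately at higher intensity would therefore remain a separate event with an on-treatment onset and would fall in A.
5. The subject has no other on-treatment event in the same table row, because "All analyses of AEs will be based on the number of subjects with AEs and NOT on the number of AEs".

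**Step 4: illustrative size.** The documents give neither a rate of pre-dose events nor a rate of worsening. Assume a denominator of 74, the approximate planned number for each treatment in the protocol synopsis, and let k be the number of patients who meet all five conditions in a given row. The reported incidence in that row then falls by 100 × k / 74 percentage points:

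- k = 0: 0
- k = 1: 100 × 1 / 74 = 1.35
- k = 5: 100 × 5 / 74 = 6.76

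The values of k are assumptions chosen to show a scale. They are not estimates.

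**Step 5: assignment to a treatment.** Protocol 7.3.4 assigns events to the first or second treatment by onset at or after the start of treatment. An event in B has its onset before that, so the protocol calls it treatment-emergent without saying which treatment it belongs to. It also speaks of deterioration under treatment and does not say whether deterioration in the REP counts.

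**The case against.** **Worsening may be recorded as a new event.** Protocol 5.3.6.2 asks sites to record deterioration of the disease under study, or of other pre-existing illness, as an adverse event, and the merging rule keeps records of different intensity apart. Where sites do this, nothing is lost. This stands as a real reduction of the problem. It does not remove it, because neither document expressly tells sites to open a new record for an event that began after consent and is still running at first dose. If worsening always produced a new onset date, the second part of the protocol's definition would be unnecessary.

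**The SAP may be abbreviating.** It says that it is based on Section 7 of the protocol, speaks of events occurring and not of onset, and refers further detail to sponsor standards that are not available here. The omission may therefore be unintended. But if occurring includes events still in progress, an event open at first dose fits both screening and treatment, and the SAP has no rule to decide between them. Standards that contained the worsening rule would conflict with the SAP's explicit screening wording.

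**The respiratory scenario is narrow.** A reader might infer that withdrawing maintenance therapy will produce a stream of exacerbations that begin in run-in and then disappear from the tables. The documents do not support that. Exclusion criterion 4 and the rescheduling rules in protocol 6.1 remove patients with an exacerbation or respiratory tract infection before randomisation, and protocol 6.2.1 bars randomising patients whom the investigator judges not stable enough. Milder respiratory events and non-respiratory events remain possible.

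**The stakes are low.** The trial is exploratory and its safety analysis is descriptive, without hypothesis tests. This is correct, and it limits the point to a minor one.

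**Conclusion.** The conflict between protocol 7.3.4 and SAP 6.1 and 7.8.1 is real and undeclared. Its consequence is that treatment-emergent events may be under-counted. The direction is fixed if an event is taken to occur at its onset. The size cannot be estimated, and the 1.35 percentage points per patient only shows scale under an assumed denominator of 74. No efficacy result changes. The documents give no basis for saying that a loss would fall more on one treatment than on the other.

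Two stronger conclusions are tempting and not supported. One is that events will certainly be lost: that depends on how sites record worsening and on whether the subject has another event in the same row. The other is that protocol 7.3.4 already settles which treatment a worsened pre-dose event belongs to, or already covers worsening in the REP. It does neither, so copying its sentence into the SAP would leave the derivation incomplete.

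**What to change.** Before unblinding, amend SAP 6.1 and 7.8.1 as follows:

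- Carry over the rule of protocol 7.3.4: an event that starts before first intake and deteriorates under treatment is treatment-emergent and is not assigned to screening.
- Say how worsening is identified in the data, for example by a recorded increase in intensity or a change to serious.
- Add, as a new rule that the protocol does not contain, that such an event is assigned to the treatment being taken when it worsened.
- State whether worsening during the REP counts.

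If the sponsor prefers assignment by onset alone, SAP Section 4 should declare it as a change from protocol 7.3.4.

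The cost is a sentence or two and a minor change to the derivation. Treatment-emergent counts may rise slightly. If worsening is not captured as a dated change, sites may have to be queried about events open at first dose.
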